2.2.4 Secondary Objective 4: Cyto-, Histopathological and Tumorgenetic markers

- SO4a: Are there potential protein- or gene-expression profiles, capable of determining the nature of the FNAC-indeterminate nodes (cytology).
- SO4b: What is the interaction/correlation between the parameters mentioned in SO4a and the results of the FDG-PET/CT scan and the final diagnosis?
 - Can these tissue molecular biomarkers help in selecting the patients that benefit most from FDG-PET, or vice versa?
 - Can higher pre-operative diagnostic accuracy be achieved by combining FDG-PET and molecular biomarkers?
 - Are molecular biomarkers related to false-positive or false-negative FDG-PET/CT results?

EFFECTS

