8.1.2 Secondary study parameters/endpoints

Secondary treatment outcome parameters (SO1, §2.2.1, p30):

- Complication fraction
 - Complications include: bleeding (requiring intervention or prolonging admission), infection (requiring intervention or prolonging admission), re-operation, ICUadmission, (temporary) hoarseness, (temporary) thyroid hormone suppletion or calcium/vitamin D suppletion.
- FDG-PET/CT diagnostic accuracy,
 - True-positive
 - True-negative
 - o False-positive
 - o False-negative
- Fraction of extra diagnostics due to coincidental FDG-PET/CT-findings,
- (Overall Survival and Disease Free Survival determined when last study-related followup of last included patient has been completed),
- Description of factors hampering implementation,
- As this study is performed intention-to-treat: the fraction and reasons of patients in the experimental study arm that still want a hemithyroidectomy despite a negative FDG-PET/CT scan.

Secondary HRQoL outcome parameters (SO2, §2.2.2, p30):

- Personal assessment in all domains of the EQ-5D-5L, the RAND-36 v2.0 (validated translation of the SF36-II), the ThyPRO and the Distress Thermometer (without the problem list) (including temporal relation),
- From the utility (EQ-5D-5L index) and overall survival, the number of QALYs are determined.

Secondary costs and cost-effectiveness parameters (SO3, §2.2.3, p31):

- Volumes of care including hospitalization days,
- iNMB (using QALYs saved as effect) including sensitivity analysis,
- iNMB (using unbeneficial treatment prevented as effect),
- Results of the iPCQ and iMCQ domains, including sick leave days.

Secondary tissue (nodule) parameters (SO4, §2.2.4, p31):

Performed on all (benign and malignant) resected lesions:

- US features (size, border, halo, calcifications, etc.)
- FDG-PET/CT features (SUV_{max}, SUV_{peak}, SUV_{mean}, metabolic volume, TLG)
- Cytological morphological features (Bethesda criteria, atypia, etc.)
- Histological morphological features (diagnosis, invasiveness, stage, atypia, etc.)
- Cytological and histological immunohistochemical features ((semi)quantitative: e.g. GLUT, HK, CA-IX, HIF-1α, Ki67/MIB, caspase-3, galectin-3, Tg, CD3, CD31/34)
- Cytological (tumour)genetic features and biomarkers: genetic profiling for gene alterations (mutations, fusions, rearrangements), gene expression, miRNA expression, and copy-number variations using next-generation sequencing and/or multigene classifier.

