8.3.5 Tissue genetic analysis

All cytology specimens will be genetically profiled using various molecular biomarkers. These tissue markers will include point mutations (e.g. BRAF and RAS point mutations), gene fusions and gene rearrangements (e.g. RET/PTC and PAX8/PPARγ rearrangements), gene and miRNA expression profiling, and copy-number variations, and possibly immunocyto- and immunohistochemical markers.

Testing techniques for molecular tissue biomarkers are rapidly developing globally. Nonetheless, as mentioned in a previous paragraph, these techniques are not yet available at Radboudumc (§1.10 Laboratory infrastructure and available techniques).

We will perform molecular diagnostics at the Leiden University Medical Centre (LUMC) (at the pathology lab of prof. dr. [name]) using state of the art next generation sequencing techniques and biomarker panels. For this purpose, cytology slides from all study participants will be sent to the LUMC. Informed consent was obtained from the study participants for these analyses.

Molecular testing on cytology requires the extraction of ± 20 ng of DNA/RNA from the existing cytology slides. To extract sufficient nucleotides, part of the cytological material will be scraped of one or two cytology slides from each patient. Prior to DNA/RNA extraction, all cytology slides

will be scanned and digitally stored; these images will be made available to and saved at the hospital where the FNA was performed, in order to enable any desired morphological review of cytology in the future. This method is also regularly used in a clinical setting. Destruction of (parts of) cytology slides disables any further staining, immunocytochemistry or other cytology testing in the future. However, as cytology review has already been completed at that point in the current study and the individual patient's treatment has been determined and executed (i.e. most patients will have undergone surgery), this will have no consequences for individual patient.

If appropriate, some cytology and histology samples may additionally be selected for further molecular testing at LUMC. This may e.g. concern Hürthle cell lesions and any copy number variations detected.

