Obtained genetic profiles will be matched to the histopathological diagnosis and characteristics, to (pre-operative) clinical characteristics and to the results of the FDG-PET/CT scan, in order to evaluate underlying associations. Moreover, we would like to evaluate potential additional (molecular) tests that could enhance FDG-PET/CTs specificity (and sensitivity).

Results of the tissue genetic analysis on cytology are not used to determine patient management, but solely for investigative/explorative purposes. However, if the result of the gene expression classifier or any additional genetic testing would show a high or definitive risk of malignancy, in a patient that did not undergo diagnostic surgery (i.e. the patient was randomized to the experimental study arm with a negative FDG-PET/CT (possible false-negative) and was advised watchful-waiting instead of surgery, or the patient chose not to undergo surgery for other reasons), the patients' treating physician will be informed of the genetic results and advised to undertake appropriate action (i.e. further diagnostics or advise to undergo surgery).

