10.4 Multivariate analysis

Where appropriate, multivariate analysis will be performed to show the independent contributions of various factors to a single event or outcome. By this means, factors are explored contributing to FDG-PET/CT false negativity, FDG-PET/CT uptake (SUV), (overall and disease-free) free survival, etc. Multivariate modelling will be performed based on the characteristics of the individual data, candidate variables must show univariate significant association. Iterative forward (1 to many) and backward (many to 1) models will be evaluated based on thresholds for in- and exclusion. See Table 10, p68.

Scale of Independent:	Scale c Dependent:	of	Observations:	Confounding Independent:	Model:
Nominal	Nominal		Censored		Kaplan-Meier
			Not censored	Yes	Mantel-
					Haenszel
				No	Log-Linear
	Numerical		Censored		Cox
					Proportional
					Hazard
			Not censored		ANOVA
Nominal &	Nominal		2-values		Logistic
Numerical		dependent		Regression	
			(binary)		
			≥3 values		Classification
			dependent		methods
	Numerical		Censored		Cox
					Proportional
					Hazard
			Not censored	Yes	ANCOVA
				No	Multiple
					Regression

Table 10: Models for assessment of independency in multivariate modelling.

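### Applied to SO4a/SO4b, the univariate screen and stepwise selection of section 10.4 would choose markers and measure PET-plus-marker accuracy on the same roughly 34 cancers, biasing the apparent gain over PET upward

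*Protocol*

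**What the plan says.** Section 2.2.4 (SO4a and SO4b) looks for protein or gene-expression profiles that reveal the nature of the nodule, and asks "Can higher pre-operative diagnostic accuracy be achieved by combining FDG-PET and molecular biomarkers". Section 8.3.5 repeats the aim: "we would like to evaluate potential additional (molecular) tests that could enhance FDG-PET/CTs specificity (and sensitivity". Section 1.7 counts the stepwise combination of tests, with its cost-effectiveness, among the secondary objectives.

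The modelling rule is in section 10.4: "candidate variables must show univariate significant association", followed by "Iterative forward (1 to many) and backward (many to 1) models will be evaluated based on thresholds for in- and exclusion". No numerical thresholds are given. On outcomes, the section says that "factors are explored contributing to FDG-PET/CT false negativity, FDG-PET/CT uptake (SUV), (overall and disease-free) free survival, etc". Its Table 10 assigns logistic regression to a binary outcome with mixed predictors.

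The candidate pool is described in two places. Section 8.1.2 gives protein markers as examples: "GLUT, HK, CA-IX, HIF-1α, Ki67/MIB, caspase-3, galectin-3, Tg, CD3, CD31/34". Section 8.3.5 adds: "These tissue markers will include point mutations (e.g. BRAF and RAS point mutations), gene fusions and gene rearrangements" and "gene and miRNA expression profiling, and copy-number variations, and possibly immunocyto- and immunohistochemical markers". No upper limit is set. The protocol names no primary marker or locked score for SO4, and no internal validation.

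**The concern.** Screening by univariate p-value and then selecting stepwise keeps the markers that happened to look good in this sample. If the accuracy of PET plus those markers is computed on the same patients, part of the gain over PET reflects the selection and would not appear in new patients. Few events and many candidates make this worse.

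The answer to SO4b is at stake, and with it the PET-plus-molecular strategy that section 1.7 wants to explore. This is separate from the scarcity of false-negative scans (132 x 3/225, about 1.8 expected). For malignancy there are enough events to fit a model, but the accuracy read from that model would be optimistic.

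**Working it through.** **Plan's own figures.** The protocol states no sample size, power or error rate for SO4; the 132 patients come from the primary comparison. Appendix IV pools 55 true positives, 80 true negatives, 87 false positives and 3 false negatives. Prevalence is (55 + 3)/225 = 25.8%, the complement of the 74.2% benign in section 4.4. Sensitivity is 94.8% and specificity 47.9%.

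**Events.**
- All patients: 132 x 58/225 = 34.0 cancers.
- After the 15% data loss of section 4.4: 34.0 x 0.85 = 28.9.
- Among the roughly 100 operated patients (section 3): 34.0 - 88 x 3/225 = 32.9.
- Section 10.1 allows no imputation, so a multivariable model uses complete cases only.

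**PET alone.** For a binary test, AUC = (sensitivity + specificity)/2 = (0.948 + 0.479)/2 = 0.71.

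**Candidates.** The count of about 18 is made up of:
- ten protein entries in section 8.1.2;
- five gene alterations (BRAF, RAS, RET/PTC and PAX8/PPARγ in 8.3.5; TERT in 13.2);
- three open-ended classes (gene expression, miRNA expression, copy number), taken as one score each.

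Figures of 30 to 50 are an assumption about how far those classes expand.

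**Screen.** With M independent noise markers tested at 0.05, the chance that at least one passes is 1 - 0.95^M.

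**Final model.** This was simulated with n = 132, 34 cancers expected, PET kept in, noise markers, a univariate screen at p<0.05, then forward or backward selection at an assumed 0.05. There were 300 to 600 runs per setting, so the Monte Carlo standard error is 2 to 3 percentage points. Ranges cover the selection direction and the mix of binary and continuous markers.

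| Noise candidates | Screen, 1 - 0.95^M | At least one retained |
|---|---|---|
| 5 (gene alterations only) | 23% | 5-9% |
| 8 (plus three profile scores) | 34% | 12-15% |
| 10 | 40% | 25-28% |
| 18 (plus ten proteins) | 60% | 35-49% |
| 24 | 71% | 50-61% |
| 30 | 79% | 57-65% |
| 48-50 | 91-92% | 78-83% |

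The first two rows fall well below the screen formula because they contain rare mutations (assumed frequencies 3-25% in the lower figures), which seldom reach p<0.05 on Fisher's test. Correlation also lowers the figures. At a correlation of 0.3, about 30% of runs retain a marker at 18 candidates and 43-46% at 24.

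**Size of the bias.** When a noise marker is retained, apparent AUC rises by 0.07 to 0.10 on average. Mean apparent AUC = 0.7135 + share retained x rise:
- 18 candidates: 0.7135 + 0.487 x 0.088 = 0.756 (all continuous); 0.7135 + 0.422 x 0.077 = 0.746 (half binary). About 0.75.
- 30 candidates: 0.7135 + 0.648 x 0.093 = 0.774; 0.7135 + 0.568 x 0.082 = 0.760. With backward selection, 0.77.

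In 4,000 simulated new patients the selected models had an AUC of 0.71, so the true gain is zero.

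**The case against.** Section 10.4 applies where appropriate and names false negativity, SUV and survival; malignancy comes in only through its general wording and the closing etc. Section 10.3 covers diagnostic accuracy with sensitivity, specificity and ROC curves. Nowhere does the protocol say that a stepwise model's apparent AUC will be reported as the combined accuracy. This stands, so the point has to be conditional on 10.4 being applied to SO4. It is still the only multivariable rule in the document, and its Table 10 points to logistic regression for a binary outcome such as malignancy.

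A reader might infer that dozens of markers are screened and that pure noise would usually look useful. The documents do not support this. The quoted question concerns pre-operative molecular markers. PET and ultrasound features are not such markers, and stains on resected tissue cannot enter a pre-operative test. Immunostaining is only a possibility in 8.3.5, and a multigene classifier could count as one result. On the named entries the share stays below one half; a majority needs about 24 or more independent candidates.

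Pure noise is also a worst case, since section 13.2 treats BRAF and TERT as specific for malignancy. The protocol calls the genetic work exploratory, and neither SO3 nor section 10.6 includes a PET-plus-marker strategy. These facts limit the consequences, but an exploratory label does not remove the bias from an apparent AUC.

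Validation detail may sit in an analysis plan that is not shown. The criticism therefore rests on the selection rule the protocol does fix, which such a plan would inherit.

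**Conclusion.** The point holds as a conditional one. If the 10.4 rule is applied to SO4a/SO4b, marker selection and accuracy measurement share about 34 cancers, and the apparent gain over PET is biased upward. Under p<0.05 and pure noise, a useless marker is retained in roughly 10-15% of analyses with the named alterations and profile scores, 35-50% with about 18 named entries, and 60-80% with 30-50 independent candidates. Mean apparent AUC is about 0.75 at 18 candidates and 0.77 at 30, against a true 0.71.

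The thresholds, the candidate count, independence and the absence of any real signal are all assumptions. The direction of the bias does not depend on them, but its size does. The finding concerns an exploratory secondary objective and leaves the primary comparison untouched. It is worth correcting because the correction is cheap.

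**What to change.** For SO4a/SO4b, replace the univariate screen and stepwise selection in section 10.4 with the following:
- Fit one penalised logistic model for malignancy (ridge, lasso or Firth), with the PET result always included.
- Admit only markers available before surgery as candidates.
- Repeat every selection and tuning step inside a bootstrap.
- Report the optimism-corrected AUC and the corrected gain over PET alone, beside the apparent values if wished.
- Label the result hypothesis-generating.

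The cost is a few lines of wording and some computing, with no change to patients, visits or samples. The downside is that the reported marker gain will look less favourable.

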3. STUDY DESIGN

A partially-blinded, prospective, multi-centre, block-randomised controlled trial (RCT) is designed. After obtaining written informed consent, patients are registered centrally, FNAC is reviewed centrally and thereafter patients are randomised to either the experimental study-arm (arm A: FDG-PET/CT driven management decisions) or a control study-arm (arm B: surgery regardless FDG-PET/CT result) using a 2:1 allocation ratio. The latter is performed both for methodological purposes (the treatment of the subjects in the control study arm is well investigated and described before) and to satisfy the assumption that patient prefer the experimental study-arm. The result of randomization is blinded to the treating physicians and central FDG-PET/CT review committee. Allocation is adaptively stratified using the minimisation method on the centre of inclusion and the most prognostic features of DTC known at this stage of patient work-up: (US) lesion size (0-10 mm/11-20 mm/21-40 mm/40+ mm), patient sex, patient age (<45yr, \geq 45yr) and Bethesda classification according to central review committee (atypia of unknown significance/follicular lesion of unknown significance (III) or (suspicion) for a follicular neoplasia (IV)).

Based on the study arm allocation and PET result, treating physicians will either be told to cancel scheduled diagnostic thyroid surgery (allocation to the experimental arm with a negative FDG-PET/CT at central review or ~32/132 patients) or to proceed with surgery (all other cases or 100/132 patients). In case surgery is cancelled the patients need to be followed-up by watchful waiting and a confirmatory ultrasonography (including FNAC) after 12 months. Patient allocation will not be disclosed to prevent study withdrawal, however in case surgery is cancelled unblinding is unavoidable (~25% of all included patients).

The Gold Standard is histology, revised by a (central) dedicated pathologist panel, obtained from surgery or 12-months follow-up, including US (+FNAC). All patients will be followed for at least 12 months after FDG-PET/CT to ensure all direct costs and complications are noted. Five years after inclusion of the last patient, long-term follow-up will be determined based on patient file review and contact with the general practitioner (flowchart Figure 1, p34 and

Table 2, p35). To ensure study results are representative for clinical use and to improve inclusion-rates, this study will be performed in both university and regional hospitals (Table 1, p33, §15.1, Appendix I: Participating Centres and Site Managers, p89 and §15.2, Appendix II: Signed Document of Cooperating Centres, p90).

Centre:	Estimated Eligible patients				
Amsterdam MC, Amsterdam	~20-30				
Erasmus MC, Rotterdam	~24				
Leiden University MC, Leiden	~15-25				
Maastricht University MC, Maastricht	~15				
RadboudUMC, Nijmegen	~20-25				
University MC Groningen, Groningen	~20-25				
University MC Utrecht, Utrecht	~12-24				
Vrije Universiteit MC, Amsterdam	~13-19				
Meander MC, Amersfoort	~25				
Hagaziekenhuis, Den Haag	~10-15				
OLVG Lucas Andreas, Amsterdam	~10-15				
Rijnstate, Arnhem	~10-15				
St. Antonius, Nieuwegein	~10-15				
Isala, Zwolle	~10				
Reinier de Graaf Gasthuis, Delft	~10				
Total:	~254				

Table 1: Participating hospitals and their estimated number of eligible patients

[figure not shown]

Figure 1: Flow-chart of the trial

Procedure:	Before	During Investigation		Follow-up				
	inclusion	Arm	Arm			 		
		А.	В.	direct	3то	6mo	12mo	1-5yr
			istory:					
Medical History							$\sqrt{2}$	(√)
Pregnancy status ¹								
	Examina	ation:						
Complete clinical								
examination								
including palpation of	\checkmark						$\sqrt{2}$	(√)
thyroid gland and								
cervical lymphnodes								
Additional investigations:								
Laboratory (incl. TSH/fT4)	\checkmark							(√)
US of thyroid and	1						1. 0	
cervical lymphnodes							√ * ,2	(√)
FNAC							√*,1,2	(√)
Central Cytology								
Review	$\sqrt{*}$							
Thyroid scintigraphy	$\sqrt{1}$							(√)
Blinded H&N FDG-		√*	√*					
PET/CT		ν"	ν"					
Additional test ⁴	-	-	-	-	-	-	-	(√)
			atment:					
Diagnostic Surgery		$\sqrt{3}$						
Cryopreservation of		√1,3	$\sqrt{1}$					
sperm		N, Y	N.					
Therapeutic Surgery		√1,3	$\sqrt{1}$					
+ RIA			N					
Histopathology		$\sqrt{3}$						
	ſ	(	 Other:	1	,			
Sick leave recall		,	,	ļ,	√*	,		
HRQoL		√*	√*	$\sqrt{*}$	√*	√*	√*	
Tissue Analysis		$\sqrt{*}$	$\sqrt{*}$					
Genetic Analysis		√*	$\sqrt{*}$					

Table 2: Summary of Protocol Investigations/Procedures. FNAC: fine-needle aspiration cytology; fT4: free thyroxine; FDG-PET/CT: Positron Emission Tomography using FDG of head, neck and upper thorax; RIA: radioiodine ablation using ¹³¹I; TSH: thyroid stimulating hormone; US: ultrasonography; ¹only on indication; ²only in FDG-PET/CT negative patients in arm A; ³only in FDG-PET/CT positive patients in arm A, ⁴Additional tests such as geneexpression classification, mutational marker panel, US elastography are allowed in the mid- to longterm follow-up at the instigation of the treating physician (but are not reimbursed by the study funds). *Part of study protocol, reimbursed by study funds.

4. STUDY POPULATION

4.1 Population (base)

All adult patients that undergo cytological evaluation of a thyroid nodule in one of the hospitals recruiting patients for this multicentre trial are potentially eligible. Feasibility taking into account the prevalence of the disorder under investigation is described in §4.5, p40.

4.2 Inclusion criteria

In order to be eligible for participation, a subject must meet ALL of the following criteria:

- Documented history of a solitary thyroid nodule or a dominant nodule within multinodular disease, with (*US-guided*) FNAC performed by a dedicated radiologist or experienced endocrinologist or pathologist, demonstrating an indeterminate cytological examination (i.e. Bethesda category III or IV, §15.3, p91) according to the local pathologist and confirmed after central review (§8.2.1, p46);
 - If a core needle biopsy was performed instead of a FNAC, the patient is eligible if the biopsy procedure was felt to be minimally disruptive to the nodule architecture, based on a review by the principal investigator or nuclear medicine investigator.
- Scheduled for surgical excision (preferably) within 2 months of the inclusion date;
- Age \geq 18 years;
 - This disease is rare in children and therefore the study will be limited to adults.
- Euthyroid state with a serum TSH or a free T4 level within the institutional upper and lower limits of normal, measured within 2 months of registration. In case of a suppressed TSH: a negative ¹²³I, ¹³¹I or ^{99m}TcO₄⁻ scintigraphy must be available ("cold nodule");
 - Mild deviations from the institutional normal limits may be considered acceptable if the patient has achieved a clinically euthyroid state with medication at a stable dose for >3 months, and the TSH is considered to be at target by the patient's treating physician. In patients with hyperthyroidism requiring treatment, this euthyroid state may be achieved with administration of a thionamide prior to FDG-PET/CT exam.
 - Patients with active (according to treating physician) hyperthyroid inflammatory conditions such as thyroiditis (e.g. m. Graves, Hashimoto, deQuervain, etc.) and toxic multinodular goitre often exhibit increased glucose uptake resulting in diffuse uptake of FDG which may obscure visualization of a thyroid tumour. These patients are not eligible for participation due to an expected higher false-negative rate.
- In patients with multinodular disease and a dominant nodule, the nuclear medicine physician responsible for FDG-PET/CT scan interpretation must determine whether the nodule is likely to be discriminated on FDG-PET/CT imaging prior to enrolment;
- Willing to participate in all aspects of the study;

 confirmed by a signed and dated written informed consent obtained from the patient (or the patient's legally acceptable representative) prior to study participation.

